Return of eDiary										X 9				X 9		8.1.3.1
Participant assessments of ef	ficacy and	health	-rela	ted q	uality	of li	fe dur	ing tri	ial visi	ts						
HEIS		X	X	X	X	X	X	X	X	X			X	X		8.1.3.3
DLQI		X	X	X	X	X	X	X	X	X			X	X		8.1.3.2
EQ-5D-5L		X			X	X	X	X		X			X	X		8.1.3.4
TSQM					X		X			X			X	X		8.1.3.5
WPAI-CHE		X			X		X			X			X	X		8.1.3.6
PGI-S ¹⁰		X		X	X	X	X									8.1.3.7

	Screen-										Follow-	Pregnancy	Primary	Nominal	Unscheduled	Protocol
	ing			Tre	eatme	nt pe	riod			EOT/ ET ¹	up 2	follow-up ³	endpoint visit at Week 12, if	Week 24 visit, if applicabl	visit, if applicable ⁵	section
Visit	1	2	3	4	5	6	7	8	9	10	11	12	applicable ⁴	e ⁴		
Week	-4 to -1	0	1	2	4	8	12	16	20	24	2 weeks	5 weeks				
Day	-28 ⁶ to -7	1	8	15	29	57	85	113	141	169	after last dose	after last dose				
Visit window (days)	-	-	±3	±3	±3	±3	±3	±3	±3	±3	±3	+6				
PGI-C ¹¹				X	X	X	X									8.1.3.8
Participant assessment of safe	ety															
Participant assessment of local tolerability (delgocitinib group only)			We	eekly	while	on tr	eatme	nt ¹²		X						8.2.7.1
Unblinded investigator assess	ments of s	safety														
Physical examination	X									X					(X)	8.2.1
Vital signs	X	X								X					(X)	8.2.2
ECG	X		X							X					(X)	8.2.3
Fasting ¹³ triglycerides and cholesterol (central laboratory)	X	X			X	X	X	X	X	X	X				(X)	8.2.4, 10.2
Chemistry, haematology (central laboratory) 13	X	X			X	X	X	X	X	X	X				(X)	8.2.4, 10.2
Serology, total IgE (central laboratory)	X															8.2.4, 10.2
Urinalysis (urine dipstick)	X	X				X	X	X		X					(X)	8.2.4, 10.2
Urine pregnancy test (WOCBP only)	X	X			X	X	X	X	X	X	X 14	X ³	X	X	(X)	8.2.5, 10.2
Check contraception compliance (alitretinoin group only)	X	X			X	X	X	X	X	X	X	X	X	X	(X)	8.2.5
Mental health interview ¹⁵	X	X			X	X	X	X	X	X					(X)	8.2.6

	Screen- ing			Tre	atme	nt pe	riod			EOT/ ET ¹	Follow- up ²	Pregnancy follow-up ³	Primary endpoint visit at Week 12, if	Nominal Week 24 visit, if applicabl	Unscheduled visit, if applicable ⁵	Protocol section
Visit	1	2	3	4	5	6	7	8	9	10	11	12	applicable ⁴	e ⁴		
Week	-4 to -1	0	1	2	4	8	12	16	20	24	2 weeks	5 weeks				
Day	-28 ⁶ to -7	1	8	15	29	57	85	113	141	169	after last dose	after last dose				
Visit window (days)	-	-	±3	±3	±3	±3	±3	±3	±3	±3	±3	+6				
Local tolerability according to investigator (delgocitinib group only)			X	X	X	X	X	X	X	X					(X)	8.2.7.2
AEs	X	X	X	X	X	X	X	X	X	X	X		X	X	X	8.3, 10.3
Optional assessments (at selec	cted sites o	only)														

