- 9. Not applicable at the ET visit if the participant does not withdraw from the trial, as participants who discontinue IMP but remain in the trial will continue completing the eDiary until the nominal Week 24 visit.
- 10. Includes Itch PGI-S, Pain PGI-S, and HESD PGI-S.
- 11. Includes Itch PGI-C, Pain PGI-C, and HESD PGI-C.
- 12. While on treatment with delgocitinib cream 20 mg/g, local tolerability will be evaluated weekly by the participants in the eDiary from Day 7 onwards up to End of Treatment/Early Termination visit.
- 13. Participants should be fasting for at least 8 hours prior to collection of laboratory samples.
- 14. For WOCBP treated with delgocitinib, only.
- 15. After baseline, mental health interview is required only for the alitretinoin group.
- 16. Photography will require additional informed consent. If deemed necessary (e.g. in case of poor quality), photographs can be retaken at the next visit.
- 17. An end-of-trial form must be completed for all screened participants at the participant's last trial visit. For participants who discontinue IMP prematurely, the end-of-trial form will be completed at the nominal Week 24 visit, if this visit occurs after Visit 11 or Visit 12 (if applicable). For WOCBP treated with alitretinoin, the end-of-trial form must be completed at Visit 12 (pregnancy follow-up). For all other participants, the end-of-trial form must be completed at Visit 11 (follow-up).

Abbreviations: AE=adverse event; CHE=chronic hand eczema; DLQI=Dermatology Life Quality Index: ECG=electrocardiogram; eDiary=electronic diary; EQ-5D-5L=EuroQoL 5-Dimension Health Questionnaire 5-Level; EOT= end-of-treatment; ET=early termination; HECSI=Hand Eczema Severity Index; HEIS=Hand Eczema Impact Scale®; HESD=Hand Eczema Symptom Diary®; IGA-CHE=Investigator's Global Assessment for chronic hand eczema®; IgE=immunoglobulin E; IMP=investigational medicinal product; PGI-C = Patient Global Impression of Change; PGI-S = Patient Global Impression of Severity; TSQM=Treatment Satisfaction Questionnaire for Medicine; WOCBP=woman of childbearing potential; WPAI-CHE=Work Productivity and Activity Impairment – Chronic Hand Eczema.

2 Introduction

Delgocitinib is a pan-Janus kinase (JAK) inhibitor that is being developed as a cream for the treatment of inflammatory skin disorders, such as CHE.

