Phototoxicity	Refer to alitretinoin product information.	Participants will be instructed to avoid excessive exposure to sunlight or sunlamps and to use sun protection (see Section 5.3.1). The use of tanning bed and phototherapy is forbidden at least 28 days before the first dose and until the end of the trial (see Section 6.8.3).
Psychiatric disorders	Refer to alitretinoin product information.	Patients with psychiatric disorders within the last year or current self-reported depression or mood disturbance will be excluded from the trial (exclusion criterion 11). Mental health will be monitored during the treatment period (see Section 8.2.6) and a specific discontinuation criterion is defined in case of mental health issues (see Section 7.1).
Lipid metabolism	Refer to alitretinoin product information.	Participants with uncontrolled hypercholesterolemia and hypertriglyceridemia will not be enrolled in the trial. (exclusion criteria 6.c and 6.d) Fasting triglycerides and cholesterol parameters will be monitored every 4 weeks during treatment and 2 weeks after the last dose (see Section 8.2.4) and participants with increased lipids that cannot be controlled at an acceptable level are required to discontinue alitretinoin (see Section 7.1).

Potential Risk of Clinical Significance	Summary of Data/Rationale for Risk	Mitigation Strategy
Male fertility	Based on non-clinical findings, the male fertility may be compromised by treatment with alitretinoin. No effects on male or female reproductive parameters were observed at the highest dose tested which reached similar plasma concentrations as those observed in humans. As with other retinoids, reversible effects on male reproductive organs were observed in experimental animals in the form of disturbed spermatogenesis and associated degenerative lesions of the testes. The safety margin in dogs with regard to the no-effect level of toxicity to male reproductive organs was 1-6 for a human dose of 30 mg	If a male is planning to reproduce during the treatment, he should be made aware that his fertility could potentially be reversibly compromised during the treatment period. The information should be given prior to enrolment and stated in the ICF.

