7.3 Loss to Follow-Up

A participant will be considered lost to follow-up if they repeatedly fail to return for scheduled visits and are unable to be contacted by the trial site.

The following actions must be taken if a participant fails to return to the clinic for a required trial visit:

[figure not shown]
- The site must attempt to contact the participant and reschedule the missed visit as soon as possible (and within the visit window, where one is defined), counsel the participant on the importance of maintaining the assigned visit schedule, and ascertain whether the participant wishes to and/or should continue in the trial.
- In cases in which the participant is deemed lost to follow-up, the investigator or designee
 must make every effort to regain contact with the participant (where possible, 3 telephone
 calls and, if necessary, a certified letter to the participant's last known mailing address or
 local equivalent methods). These contact attempts should be documented in the participant's
 medical record/CRF.
- Should the participant continue to be unreachable, he/she will be considered to have withdrawn from the trial.

8 Trial Assessments and Procedures

Trial procedures and their timing are summarised in the SoA (Table 1-1). Protocol waivers or exemptions are not allowed.

Assessments and procedures at each trial visit should be performed in the order shown in Figure 8–1.

Figure 8–1 Sequence of Assessments

Abbreviations: HECSI=Hand Eczema Severity Index; IGA-CHE=Investigator's Global Assessment for chronic hand eczema[©]; IMP=investigational medicinal product; PRO=patient-reported outcome.

Trial participants will be under careful supervision of a principal investigator who must be a dermatologist or allergist. Investigators must be experienced in treating CHE, have documented experience and completed training in use of the assessments required by the protocol, and must be a physician.

AEs must be assessed by a physician (Section 8.3).

Immediate safety concerns should be discussed with the sponsor immediately upon occurrence or awareness to determine if the participant should continue or discontinue the IMP.

Adherence to the trial design requirements, including those specified in the SoA, is essential and required for trial conduct.

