8.2.5 Pregnancy Testing

Alitretinoin is teratogenic, and there remains a risk of severe and serious malformation of the foetus in case of pregnancy even after stopping treatment. Thus, negative urine pregnancy test results must be obtained for WOCBP at screening and at baseline prior to randomisation, monthly during the trial, and 5 weeks after the last dose of alitretinoin, as shown in the SoA (Table 1-1).

For WOCBP randomised to alitretinoin, the investigator must confirm compliance to acceptable method(s) of contraception, as shown in the SoA (Table 1-1).

Similarly, for women treated with delgocitinib, negative urine pregnancy test results must be obtained for WOCBP at screening and at baseline prior to randomisation, monthly during the trial, but the last pregnancy test will occur 2 weeks after the last dose of delgocitinib, as shown in the SoA (Table 1-1).

If pregnancy occurs during the trial, treatment must be discontinued immediately, and participants treated with alitretinoin capsules should be referred to a physician specialised or experienced in teratology for evaluation and advice.

It will be recorded in the eCRF if the participant is a WOCBP and if a urine pregnancy test was performed. If not, a reason should be provided. Also, the date and the outcome of the urine pregnancy test will be recorded in the eCRF ('positive', 'negative').

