8.2.6 Mental Health Monitoring

Depression, depression aggravated, anxiety, aggressive tendencies, mood alterations, psychotic symptoms, and very rarely, suicidal ideation, suicide attempts and suicide have been reported in patients treated with systemic retinoids, including alitretinoin.

All participants treated with alitretinoin should be monitored for signs of depression and referred for appropriate treatment if necessary.

Prior to initiation of alitretinoin and at each visit during treatment, participants should be asked about any psychiatric disorder, depression, or mood disturbance in a mental health interview, as outlined in the SoA (Table 1-1).

Participants should stop alitretinoin if they develop depression, mood disturbance, psychosis, or aggression, as described in Section 7.1. However, discontinuation of alitretinoin may be insufficient to alleviate symptoms and therefore further psychiatric or psychological evaluation may be necessary. Awareness by family or friends may be useful to detect mental health deterioration.

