10.5 Appendix 5: COVID-19 Pandemic Contingency Plan

Without compromising the safety of participants and trial integrity, it is expected that efforts are made to secure attendance at sites for all visits, ensuring important efficacy and safety assessments for the trial

If on-site visits are not possible due to local authority-issued preventive measures, the affected site will postpone screening and randomisation of new participants until on-site visits can be conducted. For already randomised participants, post-baseline visits can be done remotely via phone or video. At phone/video visits, no investigator assessments of efficacy can be done, but the following data will be collected remotely, according to the SoA (Table 1-1):

- AE reporting.
- Treatment compliance (daily completion in the eDiary).
- Concomitant medication and concurrent procedures.
- HESD (daily completion in the eDiary).
- Participant assessment of local tolerability (weekly completion in the eDiary).
- PROs (DLQI, HEIS, EQ-5D-5L, TSQM, WPAI-CHE, PGI-S, and PGI-C). The participants will receive a link to complete the PROs in a web browser from their own device.
- New CHE lesions.
- Urine pregnancy test. Women of childbearing potential will receive 1 extra urine pregnancy test at the randomisation visit to keep at home in case on-site visits become impossible during the trial. The participant will perform the test at home and inform the investigator about the result via phone and to send a picture of the test to the site or show it via video. Additional urine pregnancy tests can be shipped to the participant's home together with IMP (see below) if needed.
- For participants treated with alitretinoin:
 - Serum cholesterol and serum triglycerides (fasting values) should continue to be monitored by a local laboratory, at the timepoints outlined in the SoA (Table 1-1).
 - Remote consultation to allow for adequate monitoring of mental health should be maintained at the timepoints outlined in the SoA (Table 1-1). The potential for psychiatric disorders may be increased by COVID-19 isolation measures and this may complicate the clinical picture.

In the eCRF, it will be recorded whether a visit or a given assessment was done remotely or not done. If not done, it will be recorded if this was due to the COVID-19 pandemic.

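### Section 8.2.6 asks for a mental health interview at every alitretinoin treatment visit, but Table 1-1 schedules none at Visits 3 and 4 (Days 8 and 15)

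*Combined protocol and SAP*

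**What the plan says.** Section 8.2.6 (Mental Health Monitoring) states: "Prior to initiation of alitretinoin and at each visit during treatment, participants should be asked about any psychiatric disorder, depression, or mood disturbance". The same sentence continues "in a mental health interview, as outlined in the SoA (Table 1-1"), so it sets a frequency and also points to the schedule of activities.

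In Table 1-1 (Section 1.3), the row "Mental health interview" is marked at Visits 1, 2 and 5 to 10 and is optional at unscheduled visits. It is blank at Visits 3 and 4. Its footnote 15 reads "After baseline, mental health interview is required only for the alitretinoin group". That restricts the interview by treatment group and says nothing about particular visits.

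Three other places bear on the point:

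- Table 2-1 (Section 2.3.1) lists the monitoring among the measures against psychiatric disorders on alitretinoin: "Mental health will be monitored during the treatment period (see Section 8.2.6").
- The opening text of Section 8 says "Adherence to the trial design requirements, including those specified in the SoA, is essential and required for trial conduct".
- Section 10.5, on remote visits during the pandemic, says "Remote consultation to allow for adequate monitoring of mental health should be maintained at the timepoints outlined in the SoA".

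**The concern.** The sentence and the table it cites give different schedules for the same safety check. A site that works from the table will not hold the interview on Days 8 and 15. A site that works from the sentence will. Remote visits under Section 10.5 take their timing from the table, so they inherit the blanks.

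What is at stake is early detection. Section 7.1, item 6, makes depression, mood disturbance, psychosis or aggression a mandatory reason to stop alitretinoin for good, with immediate referral. That rule works only if the symptoms come to light. Section 8.2.6 itself notes that suicidal ideation and attempts have been reported, very rarely, with systemic retinoids. Under Table 1-1, no direct question about mood is scheduled between baseline and Day 29, although the participant is on site twice in that time.

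**Working it through.** The plan gives no figure to reproduce. The check is a count of cells and days.

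**Inputs**

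- Visit days from Table 1-1: Visit 2 = Day 1, Visit 3 = Day 8, Visit 4 = Day 15, Visit 5 = Day 29, Visit 6 = Day 57, Visit 7 = Day 85, Visit 8 = Day 113, Visit 9 = Day 141, Visit 10 = Day 169. The window is ±3 days from Visit 3 on.
- Nine visits in the treatment period (Section 4.1). Visit 2 is the pre-dose baseline.
- Alitretinoin is taken continuously to Week 12 whatever the clearance status, barring safety problems (Section 6.2.1.2). Participants are therefore on drug at Visits 3 and 4.
- 255 participants per group (Section 9.5).

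**Are the blanks real?** The interview row has the same number of cells (16) as the adverse event, contraception and investigator local tolerability rows. The adverse event and local tolerability rows are marked at Visits 3 and 4. The blanks are not columns lost in reading the table.

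**Coverage**

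- Post-baseline treatment visits, Visits 3 to 10: 9 − 1 = 8.
- Marked for interview, Visits 5 to 10: 6.
- Coverage: 6/8 = 75%. Counting the baseline visit as well gives 7 of 9, with the same two blanks.

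**Time to the first interview after dosing** (first capsule on Day 1)

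- As scheduled: 29 − 1 = 28 days; ±3 gives 25 to 31 days.
- With Visit 3 marked: 8 − 1 = 7 days; ±3 gives 4 to 10 days.

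**Nominal gaps between interviews**

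| Interval | As scheduled | With Visits 3 and 4 marked |
|---|---|---|
| Day 1 to Day 29 | 28 days | 7, 7 and 14 days |
| Day 29 to Day 169 | 28 days each | 28 days each |

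The longest gap in the first four weeks falls from 28 to 14 days. The longest gap over the whole treatment period stays at 28 days.

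**Does any text exempt the two visits?** Footnote 15 does not. Where the protocol wants a roughly monthly check, it can say so. For pregnancy tests, Section 8.2.5 reads "negative urine pregnancy test results must be obtained for WOCBP at screening and at baseline prior to randomisation, monthly during the trial", and Table 2-1 gives a four-week interval for lipids. Section 8.2.6 gives no such interval.

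**The case against.** The best reply is that the sentence in Section 8.2.6 defers to Table 1-1, and that the table follows a coherent pattern. The lipid, chemistry and haematology, pregnancy test and contraception rows are also blank at Visits 3 and 4 and marked at Visits 5 to 10. Section 8.2.5 likewise leaves the timing of the contraception check to the table. Amendment 3 edited the interview row, and the current row still leaves both visits empty. A 4-weekly safety schedule may well have been the intention.

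This stands as a possible explanation. It does not reconcile the texts: a sentence that promises every treatment visit still cites a table that omits two. Nor does it show which of the two is wrong. It also cannot be taken as certain that sites will follow the table, since Section 10.1.10 requires the whole protocol to be followed.

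A reader might infer that alitretinoin participants go unmonitored for psychiatric events in the first month. The documents do not support that. Adverse events are collected at Visits 3 and 4 with an open question (Section 8.3.2), an interview may be held at an unscheduled visit, and Section 8.2.6 also calls for general monitoring for depression with no visit limit. Exclusion criterion 11 removes people with a psychiatric disorder in the past year or current self-reported low mood. What is missing from the table is the direct question, not all monitoring.

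A reader might also infer a gap in follow-up after a psychiatric stop. That is largely covered by the interview at the early termination visit, the immediate referral in Section 7.1, item 6, and the adverse event follow-up in Sections 8.3.3 and 10.3.3.

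**Conclusion.** The inconsistency is real and worth correcting. Section 8.2.6 asks for the interview at every treatment visit on alitretinoin. Table 1-1 schedules it at 6 of 8 and puts the first post-dose interview 25 to 31 days after dosing starts. The count rests only on Table 1-1; the day range also assumes a first dose on Day 1 and visits within their windows.

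The conclusion is limited. A reader might infer that 4-weekly questioning is itself inadequate, or that psychiatric risk is concentrated in the first month. The documents give no data on either, and they refer to the alitretinoin product information for this risk. The interval after Visit 5 is not challenged. The point concerns safety monitoring only: no endpoint, sample size, error rate or efficacy analysis changes.

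**What to change.** In Table 1-1, mark the mental health interview at Visits 3 and 4. Footnote 15 already confines it to the alitretinoin group after baseline, so the footnote needs no change. The cost is one table row and at most 2 × 255 = 510 short interviews, with no new visits.

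If the sponsor did intend a 4-weekly schedule, the alternative is to reword Section 8.2.6 so that it names the visits: screening, baseline, Week 4, and every four weeks to Week 24. That adds no interviews and removes the conflict. It leaves coverage at 6 of 8 and weakens the mitigation cited in Table 2-1, so marking the two visits is preferable.

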8.2.7 Local Tolerability

For participants receiving delgocitinib cream only, an assessment of local tolerability will be provided by the participant and by the investigator, according to the SoA (Table 1-1).

8.2.7.1 Participant's Assessment of Local Tolerability

The participant will complete a weekly assessment of stinging/burning in connection with the delgocitinib cream applications in the eDiary. The participant will be asked to retrospectively assess the worst stinging/burning in connection with the delgocitinib cream application during the last week. In addition, the participant will be asked by the unblinded investigator at the End of Treatment/Early Termination visit to assess the local tolerability during the last week (see Section 1.3). The assessment will be done using the 4-point scale shown in Table 8-8.

Table 8-8 Participant's Assessment of Local Tolerability after Delgocitinib Cream Application

Grade (severity)	Stinging/burning				
0 (none)	No stinging or burning.				
1 (mild)	Slight warm, tingling sensation, not really bothersome.				
2 (moderate)	Definitive warm, tingling sensation, that is somewhat bothersome.				
3 (severe)	Hot, tingling/stinging sensation that has caused definite discomfort.				

The participant's assessment of local tolerability may be reported as an AE at the discretion of the investigator, even if the investigator does not suspect a local skin reaction related to the application of delgocitinib cream (reporting of e.g. pain or stinging/burning by the participant).

For the participant's assessment of local tolerability at the EOT/ET visit, the highest (worst) skin reaction score across treatment area(s) will be recorded in the eCRF.

